This clinical investigation will be conducted in accordance with this Clinical Investigation Plan, the Declaration of Helsinki, applicable Good Clinical Practices and regulations (e.g., US 21 CFR Part 50, 21 CFR Part 56, 21 CFR Part 812 and OUS ISO14155:2011) and the appropriate local legislation(s). The most stringent requirements, guidelines or regulations must always be followed. The conduct of the clinical investigation will be approved by the appropriate Institutional Review Board (IRB)/Ethics Committee (EC) of the respective investigational site and by the applicable regulatory authorities (e.g., FDA, PMDA, MHRA, etc.).

1 INTRODUCTION

This clinical investigation is intended to demonstrate the safety and effectiveness of the TactiCath™ Contact Force Ablation Catheter, Sensor Enabled™ (TactiCath SE) for use in cardiac electrophysiological mapping and for the treatment of drug-refractory, recurrent symptomatic persistent atrial fibrillation (AF) when used in conjunction with a compatible radiofrequency (RF) generator and three-dimensional mapping system. This clinical investigation will be conducted under an investigational device exemption (IDE) and is intended to support market approval of the TactiCath SE ablation catheter for the treatment of drug refractory, symptomatic persistent atrial fibrillation in the United States. Two hundred twenty-four (224) subjects will be enrolled at up to 25 investigational sites worldwide. This clinical investigation is sponsored by Abbott and will be conducted in accordance with this clinical investigation plan (CIP).

1.1 Background and Rationale

AF is a result of multiple diseases and mechanisms that are not completely understood and will often exacerbate an underlying heart condition. AF occurs when structural and/or electrophysiological abnormalities alter atrial tissue to promote abnormal impulse formation and/or propagation.¹ Symptoms associated with AF include fatigue, palpitations, dyspnea, hypotension, syncope, and heart failure. AF often progresses from paroxysmal to persistent over a variable period of time. Patients with persistent AF have worse outcomes than for patients with paroxysmal AF and are more likely to develop potentially life-threatening problems, such as stroke, tachycardia-induced cardiomyopathy and congestive heart failure, all of which may increase mortality.^{2,3} Maintenance of sinus rhythm may confer a mortality benefit and is associated with improvements in symptoms and quality of life.

Management of patients with AF has traditionally consisted of three main components: (1) anticoagulation for stroke prevention; (2) rate control; and (3) rhythm control.⁴ Persistent symptoms associated with AF remain the most compelling indication for a rhythm-control strategy. The efficacy of radiofrequency catheter ablation for maintaining sinus rhythm is superior to current antiarrhythmic drug therapy in select patient populations.¹ The decision whether to pursue catheter ablation depends on a large number of variables, including the type of AF, degree of symptoms, presence of structural heart disease, candidacy for alternative options such as rate control or antiarrhythmic drug therapy, likelihood of complications, and patient preference.¹ Catheter ablation is considered a reasonable indication for patients with symptomatic persistent AF refractory or intolerant to at least one Class I or III antiarrhythmic medication.^{1,4} Catheter ablation may also be considered as first-line therapy in select patients before a trial of antiarrhythmic drug therapy when a rhythm-control strategy is desired.^{1,4}

The method of catheter ablation for persistent AF remains controversial.^{2,4} The strategy for ablation is often individualized based on patient characteristics, atrial fibrillation history and coexisting structural heart disease. Electrical isolation of the pulmonary veins by catheter ablation is the cornerstone for most AF ablation procedures as most triggers for AF originate from the pulmonary veins.³ Pulmonary vein (PV) isolation involves creating circumferential lesions around the veins to electrically isolate them from the rest of the left atrium. Additional non-PV ablation strategies are also often employed in patients with persistent AF to improve outcome and may consist of the following: ablation of the posterior wall of the left atrium; creating linear ablation lesions in the right or left atrium; mapping and ablation of areas of abnormal myocardial tissue; ablation of complex fractionated atrial electrograms or rotational activity; and/or ablation of autonomic ganglia.⁴ These additional non-pulmonary vein ablation strategies all have

a Class IIb recommendation (benefit of AF ablation is greater or equal to the risks and AF ablation may be considered) based on a moderate quality of evidence for these approaches.

Contact force sensing ablation catheter systems are a technology that is growing in adoption for AF ablation. Contact force sensing catheter systems provide feedback to operators regarding the force applied by the catheter tip on the cardiac wall. Recommendations for contact force catheters for atrial fibrillation ablation procedures are also defined in the 2017 HRS/EHRA/ECAS/APHRS/SOLAECE Expert Consensus on AF Ablation (Class IIa recommendation, Level of evidence C).⁴

The TactiCath family of contact force sensing catheters has been studied extensively. The early generation TactiCath catheters were investigated in the TOCCATA⁵, EFFICAS I⁶ and II⁷, and TOCCASTAR⁸ clinical trials. The next generation, TactiCath Quartz, implemented an updated contact force sensing mechanism, which was studied in the TOCCASTAR Supplemental Clinical Study. Long-term follow up data are currently being collected in the TactiCath Quartz Post Approval Study. These clinical trials have investigated the safety and effectiveness of the previous generations of the TactiCath ablation catheters for the treatment of drug refractory, symptomatic AF.⁵⁻⁸

The TactiCath SE ablation catheter is the latest TactiCath contact force sensing catheter from Abbott, which incorporates a magnetic sensor for tracking with the EnSite Precision Mapping System and utilizes a new handle and shaft to improve catheter handling. Preclinical testing has demonstrated that the TactiCath SE ablation catheter has an acceptable safety profile. Refer to the Report of Prior Investigations that summarizes the preclinical testing, the on-going post-approval study, and the literature review demonstrating the safety of this device to date.

Currently, there are no ablation catheters with an indication for use in the persistent AF population available in the United States. The PERSIST-END clinical investigation will be used to obtain regulatory approval from the Food and Drug Administration (FDA) and will utilize the latest iteration of the TactiCath™ catheter (TactiCath™ Contact Force Ablation Catheter, Sensor Enabled). The PERSIST-END trial will be one of the first clinical trials within the United States to evaluate the safety and effectiveness of a radiofrequency ablation catheter for use in the persistent AF population.

2 CLINICAL INVESTIGATION OVERVIEW

2.1 Clinical Investigation Objective

The objective of this clinical trial is to demonstrate that ablation with the TactiCath™ Contact Force Ablation Catheter, Sensor Enabled™ (TactiCath SE) is safe and effective for the treatment of drug refractory, symptomatic persistent atrial fibrillation when following standard electrophysiology mapping and radiofrequency ablation procedures.

2.2 Devices to Be Used in this Clinical Investigation

2.2.1 Name of the Device Under Investigation

The investigational device to be used in this trial is the TactiCath™ Contact Force Ablation Catheter, Sensor Enabled™ and is manufactured by Abbott. The *Instructions for Use* document is available under separate cover and will be included with each shipped product whether it is market released (geographies outside of the United States) or labeled as investigational (within the United States).

United States only:

The system to be used for the ablation procedures in this clinical trial includes the TactiSys Quartz Equipment (PN-004 400) and Ampere Radiofrequency Generator (H700488), which, when used in combination with TactiCath SE for persistent atrial fibrillation ablation, are considered investigational. The Ampere generator and TactiSys Quartz Equipment will be obtained by U.S. study sites through their usual commercial channels. A label indicating each device is considered part of an investigational system will be affixed by Abbott personnel to the Ampere RF Generator and TactiSys Quartz Equipment at sites on those devices used for ablation in the PERSIST-END trial.

The list of investigational equipment for sites in the United States and their respective model numbers are listed in **Table 1**.

Table 1. Investigational Devices

Device name	Model/Type
TactiCath™ Contact Force Ablation Catheter, Sensor Enabled™	A-TCSE-D
	A-TCSE-F
	A-TCSE-J
	A-TCSE-DD
	A-TCSE-FF
	A-TCSE-JJ
	A-TCSE-DF
A-TCSE-FJ	
TactiSys™ Quartz Equipment	PN-004 400
Ampere™ RF Generator	H700488 (US)
	H700489 (OUS)

All other geographies where TactiCath SE is commercially available:

In countries outside of the United States, the TactiCath SE is indicated for use in cardiac electrophysiological mapping (stimulation and recording), and, when used in conjunction with a radiofrequency generator for cardiac ablation of supraventricular arrhythmias in the right and left atrium, including atrial fibrillation. All devices to be used during the clinical trial are market released, and will be utilized according to approved labeling, *Instructions for Use*, and medical standard of care guidelines.

2.2.2 Ancillary Devices

The ancillary devices that will be used in this clinical investigation are listed in **Table 2**. The EnSite Precision Cardiac Mapping System, EnSite Velocity (v5.2 or equivalent) and Precision (v2.2 or equivalent) Software, Contact Force Module, and Cool Point™ Pump are not part of the investigational system and will be used as commercially indicated.

A restricted release of the commercial license entitlement kit for TactiCath SE will be provided only to sites participating in this clinical investigation under a Clinical Trial Authorization. This would allow recognition of the TactiCath SE catheter by the commercial EnSite systems at study centers and will appropriately limit use of the catheter to the clinical investigation prior to PMA approval.

Table 2. Ancillary Devices

Ancillary Device Name	Model Number
EnSite System (Amplifier and Display Workstation)	EE3000
EnSite Velocity Software v5.2 or equivalent	H702495
EnSite Precision Software v2.2 or equivalent	H702496
Ensite Precision Module, Sensor Enabled Kit	H702470
Contact Force Module	H702500
TactiCath Ablation Catheter, Sensor Enabled, Software Installation (License Entitlement)	H702517
Cool Point™ Pump, v24 or greater	IBI-89003 (US) 85784 (OUS)

2.2.3 Intended Indication for Use

The TactiCath™ Contact Force Ablation Catheter, Sensor Enabled™ is indicated for use in cardiac electrophysiological mapping and for the treatment of drug-refractory, recurrent symptomatic persistent atrial fibrillation when used in conjunction with a compatible radiofrequency generator and three-dimensional mapping system.

2.2.4 Description of the Device Under Investigation

2.2.4.1 TactiCath Sensor Enabled Ablation Catheter

The TactiCath SE is designed to facilitate electrophysiological mapping of the heart chambers and to transmit RF current to the catheter tip electrode for intracardiac ablation purposes. The catheter is used in conjunction with a RF generator, an irrigation pump, and a dispersive pad (indifferent patch electrode) when ablating. TactiCath SE is compatible with introducers or sheaths with a minimum diameter of 8.5 F. TactiCath SE is a sterile, single use catheter with a 7.5 F shaft and an 8 F distal section. It is constructed of thermoplastic elastomer material and noble metal electrodes.

TactiCath SE has novel contact force and magnetic sensors. It has a fluid lumen connected to open conduits within a 6-hole tip electrode for saline irrigation during the ablation procedure (**Figure 1**). For both uni-directional (**Figure 2**) and bi-directional catheters (**Figure 3**), the tip curvature is manipulated by the control mechanism located on the handle at the catheter's proximal end. To adjust the curve of the distal tip on the uni-directional catheter, the thumb control located on the handle may be pushed or pulled. To adjust the curve of the distal tip on the bi-directional catheter, the actuator may be used to deflect the catheter in either direction. The catheter interfaces with standard recording equipment and a compatible RF generator via the TactiSys Quartz Equipment using the optical connector and 19-pin electrical connector on the catheter. The catheters are available in eight distal curve shapes.

Figure 1. Exposed View of the TactiCath SE Tip

[figure not shown]

Figure 2. Uni-Directional TactiCath SE

Figure 3. Bi-Directional TactiCath SE

2.2.5 Device Handling and Storage

The Sponsor requires all investigational products be stored according to the labeling and *Instructions for Use* in a secure area to prevent unauthorized access or use.

In the United States, the commercially available TactiSys Quartz Equipment and Ampere generator can be stored per standard practice at each hospital. The TactiCath SE Software license will be activated by Abbott personnel on commercially available EnSite Precision units (v2.2 or equivalent software) as part of site activation for sites participating in the trial that have not activated the license.

Outside the United States, all devices will be used according to approved labeling and published medical practice guidelines. Regulations for handling of investigational devices do not apply.

3 CLINICAL INVESTIGATION DESIGN

This is a prospective, single-arm, multi-center investigational device exemption (IDE) clinical trial to evaluate the safety and effectiveness of ablation with the TactiCath SE catheter for the treatment of drug refractory, symptomatic persistent AF compared to a predetermined performance goal. A total of 224 subjects will be enrolled at up to 25 investigational sites worldwide.

[figure not shown]
[REDACTED] Subjects will be followed for 15-months after their initial ablation procedure. The primary endpoints will be evaluated when all subjects have completed their 15-month follow-up visit. [REDACTED]

[REDACTED] The pre-market approval (PMA) clinical report will be prepared after the last subject has completed their final follow-up visit.

3.1 Clinical Investigation Procedures and Follow-up Schedule

The visit schedule for subjects is shown in **Figure 4**. Subjects will be consented for the trial at baseline as specified in **Section 5.2.2**. Once eligibility is confirmed, the subject will then undergo an ablation procedure for treatment of their persistent AF condition. A blanking period of 90-days will be employed after the initial ablation procedure, followed by a 90-day therapy consolidation period and then a 9-month evaluation period for a total of 15-months of follow-up. Medication adjustments, cardioversions, and one repeat ablation procedure may be performed in either the blanking or therapy consolidation periods. It is recommended that subjects are off antiarrhythmic drugs (AADs) after the blanking and/or therapy consolidation period. Follow-up assessments will occur either in-person at the clinic or via phone contact after the procedure. The scheduled follow-up visits will occur at 7-days post-procedure (phone call), and at 3-months (in-person visit), 6-months (phone call), 12-months (phone call), and 15-months (in-person visit). The subject will be exited from the trial after completing their 15-month follow-up visit.

Figure 4. Study Flow Diagram

3.2 Measures Taken to Avoid and Minimize Bias

Multiple measures will be taken to avoid and minimize bias in this clinical investigation. First, PERSIST-END is a prospective clinical investigation in which the outcome is unknown at the time of enrollment and

all subjects must meet the defined eligibility criteria to minimize selection bias. Next, guidance will be provided to sites regarding data collection for questionnaires and the post-procedure follow-up phone calls to be performed at 7-days, 6-months, and 12-months post-procedure. Additionally, case report forms for data collection will be provided to sites, which will minimize inter-observer variability.

Evaluation of primary endpoint data will be performed by an independent core laboratory and Clinical Events Committee (CEC). Collected electrocardiogram (ECG), trans-telephonic monitoring (TTM) data, and 24-hour Holter data from sites will be evaluated by a physician at a core laboratory to determine AF recurrence for subjects. Adverse events will be adjudicated by a CEC made up of physicians who are not investigators in the trial. Although the investigators at each site will perform their own adjudication regarding outcome data, only the core lab and the CEC's adjudication of the collected data will be used for analysis in order to minimize bias.

Protocols are also in place to minimize lost to follow-up subjects and for handling missing data. Sensitivity analyses will be performed demonstrating the impact missing data may have on the trial.

3.3 Suspension or Early Termination of the Clinical Investigation

No formal statistical rule for early termination of the clinical investigation for insufficient effectiveness of the device under investigation is defined.

The Sponsor reserves the right to discontinue the clinical investigation at any stage or reduce the follow-up period with suitable written notice to the investigator.

Should the clinical investigation be discontinued by the Sponsor, subjects will be followed per routine hospital practice with device-related AEs reported to the Sponsor as per vigilance/commercial reporting requirements.

Should this occur, the investigator shall return all clinical investigation materials (including devices) to the Sponsor and provide a written statement to the IRB/EC (if applicable) as to why premature termination has taken place. All applicable clinical investigation documents shall be subject to the same retention policy as detailed in **Section 11.5** of this CIP.

A Principal Investigator, IRB/EC or regulatory authority may suspend or prematurely terminate participation in a clinical investigation at the investigational sites for which they are responsible. The investigators will follow the requirements specified in the Clinical Trial Agreement.

If the Sponsor suspends or prematurely terminates the clinical investigation at an individual site in the interest of safety, the Sponsor will inform all other Principal Investigators.

If suspension or premature termination occurs, the Sponsor will remain responsible for providing resources to fulfill the obligations from the CIP and existing agreements for following the subjects enrolled in the clinical investigation and the Principal Investigator or authorized designee will promptly inform the enrolled subjects at his/her site, if appropriate.

4 ENDPOINTS

Two primary endpoints and three secondary endpoints will be evaluated in this clinical investigation. Additional data will also be collected for assessment in this trial.

4.1 Primary Endpoint

4.1.1 Primary Safety Endpoint

The primary safety endpoint is the rate of device and/or procedure-related serious adverse events with onset within 7-days of any ablation procedure that uses the TactiCath SE catheter (initial or repeat procedure performed ≤ 180 days of initial procedure) that are defined below:

- Atrioesophageal fistula¹
- Cardiac tamponade/perforation¹
- Death
- Heart block
- Myocardial infarction (MI)
- Pericarditis²
- Phrenic nerve injury resulting in diaphragmatic paralysis
- Pneumothorax
- Pulmonary edema (respiratory insufficiency)
- Pulmonary vein stenosis¹
- Stroke/cerebrovascular accident (CVA)
- Thromboembolism
- Transient ischemic attack
- Vascular access complications (including major bleeding events³)

-
1. Atrioesophageal fistula, cardiac tamponade/perforation and pulmonary vein stenosis will be evaluated through 15-months.
 2. Pericarditis is a common occurrence for almost all procedures and will only be considered a primary safety endpoint event if the pericarditis pleuritic symptoms last longer than 7-days and/or requires hospitalization of greater than 24 hours for reasons other than for observational purposes only.
 3. Bleeding is a major complication of AF ablation if it requires and/or is treated with transfusion or results in a 20% or greater fall in hematocrit.

Definitions regarding the primary safety events are provided in **Appendix III**.

Serious AF/atrial flutter (AFL)/atrial tachycardia (AT) recurrences without coexisting conditions (e.g. thromboembolism, worsening heart failure, etc.) will be counted as effectiveness failures but will not count against the primary safety endpoint.

The performance goal is set at [REDACTED] as determined by relevant studies for persistent AF that utilize radiofrequency ablation. Refer to the Statistical Analysis Plan for details regarding the rationale for the performance goal.

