APPENDIX III. DEFINITIONS

The following definitions will be used by the CEC to determine whether the events listed below constitute a device or procedure related serious adverse event included in the primary endpoint. Most of the definitions have been adapted from the 2017 HRS/EHRA/ECAS/APHRS/SOLAECE Expert Consensus on AF Ablation.⁴

Primary Safety Event	Description
Atrioesophageal fistula	A connection between the atrium and the lumen of the esophagus. Evidence supporting this diagnosis includes documentation of esophageal erosion combined with evidence of a fistulous connection to the atrium, such as air emboli, an embolic event, or direct observation at the time of surgical repair. A CT scan or MRI scan is the most common method of documentation of an atrioesophageal fistula.
Bleeding	Bleeding is a major complication of AF ablation if it requires and/or is treated with transfusion or results in a 20% or greater fall in hematocrit.
Cardiac tamponade/perforation	The development of a significant pericardial effusion during or within 30 days of undergoing an AF ablation procedure. A significant pericardial effusion is one that results in hemodynamic compromise, requires elective or urgent pericardiocentesis, or results in a 1-cm or more pericardial effusion as documented by echocardiography. Cardiac tamponade/perforation should also be classified as “early” or “late” depending on whether it is diagnosed during or following initial discharge from the hospital.
Death	Adverse event resulting in the patient’s death.
Heart block (AV block)	New, persistent 2 nd or 3 rd degree AV block not attributable to a vasovagal reaction or medication effect and requiring permanent pacing.
Myocardial infarction	Irreversible necrosis of heart muscle secondary to prolonged ischemia with at least one of the following three criteria: (2) Detection of ECG changes indicative of new ischemia (new ST-T wave changes or new LBBB) that persist for more than 1 hour; (3) Development of new pathological Q waves on an ECG; (4) Imaging evidence of new loss of viable myocardium or new regional wall motion abnormality.
Pericarditis	Pericarditis should be considered a major complication following ablation if it results in an effusion that leads to hemodynamic compromise or requires pericardiocentesis, prolongs hospitalization by more than 48 hours, requires hospitalization, or persists for more than 30 days following the ablation procedure.

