Phrenic nerve injury resulting in diaphragmatic paralysis	Phrenic nerve paralysis is defined as absent phrenic nerve function as assessed by a sniff test. A phrenic nerve paralysis is considered to be permanent when it is documented to be present 12 months or longer following ablation.
Pneumothorax	Abnormal collection of air in the pleural space between the lung and the chest wall that prolongs the hospital stay (for observation) or requires surgical intervention or chest tube placement.
Pulmonary edema	Excess fluid in the lungs that includes all of the following: 
 • Symptoms (e.g. dyspnea) • Physical findings (e.g. rales, hypoxemia) • Radiologic findings • Response to diuretic therapy • Requires hospitalization
Pulmonary vein stenosis	Reduction of the diameter of a pulmonary vein or a pulmonary vein branch of ≥70% confirmed via imaging (CT or MRI).
Stroke / cerebrovascular accident	Stroke diagnostic criteria:

Primary Safety Event	Description
	
 • Rapid onset of a focal or global neurological deficit with at least one of the following: change in level of consciousness, hemiplegia, numbness or sensory loss affecting one side of the body, dysphasia or aphasia, hemianopia, amaurosis fugax, or other neurological signs or symptoms consistent with stroke • Duration of a focal or global neurological deficit ≥ 24 hours; OR < 24 hours if therapeutic intervention(s) were performed (e.g. thrombolytic therapy or intracranial angioplasty); OR available neuroimaging documents a new hemorrhage or infarct; OR the neurological deficit results in death. • No other readily identifiable nonstroke cause for the clinical presentation (e.g. brain tumor, trauma, infection, hypoglycemia, peripheral lesion, pharmacological influences). • Confirmation of the diagnosis by at least one of the following: neurology or neurosurgical specialist; neuroimaging procedure (MRI or CT scan or cerebral angiography); lumbar puncture (i.e. spinal fluid analysis diagnostic of intracranial hemorrhage)
Thromboembolism	An arterial or venous thrombus that results in deep vein thrombosis, pulmonary embolism, or peripheral arterial embolism.
Transient ischemic attack	New focal neurological deficit of vascular (occlusive) origin with rapid symptom resolution (usually 1 to 2 hours), always within 24 hours determined by the consulting neurologist; neuroimaging without tissue injury.

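### Protocol 4.1.1 and Appendix III give different counting rules for tamponade/perforation and for one kind of pericarditis in the primary safety endpoint, and no readable text says which governs

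*Protocol*

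**What the plan says.** Protocol 4.1.1 counts listed device- or procedure-related serious adverse events with onset within 7 days of a TactiCath SE ablation. Its footnotes modify that rule for some components.

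- **Footnote 1:** "Atrioesophageal fistula, cardiac tamponade/perforation and pulmonary vein stenosis will be evaluated through 15-months".
- **Footnote 2:** pericarditis counts only "if the pericarditis pleuritic symptoms last longer than 7-days and/or requires hospitalization of greater than 24 hours", and the hospital stay must be for more than observation.

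Appendix IV and SAP 1.4.1 repeat both footnotes. Section 4.1.1 then adds: "Definitions regarding the primary safety events are provided in" Appendix III.

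Appendix III states its own purpose. The CEC uses its definitions "to determine whether the events listed below constitute a device or procedure related serious adverse event included in the primary endpoint". Two of its rows matter here.

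- **Tamponade/perforation:** "The development of a significant pericardial effusion during or within 30 days of undergoing an AF ablation procedure".
- **Pericarditis:** a major complication if it causes haemodynamic compromise or needs pericardiocentesis, or if it "prolongs hospitalization by more than 48 hours, requires hospitalization, or persists for more than 30 days following the ablation procedure".

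Protocol 10.7.2 has the CEC work from its charter and from the CIP's definitions. Both 10.7.2 and SAP 3.2 make the CEC-adjudicated results the ones analysed.

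**The concern.** The footnotes and the appendix each claim to decide what counts, and for these two components they give different answers. The CEC is sent to the definitions in the CIP, and the CIP contains both. In a single-arm trial judged against a fixed performance goal, the event count decides the test. If the rule is not settled before the count is known, it may end up being chosen with the result in view, or applied differently from case to case.

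**Working it through.** **1. Tamponade/perforation, texts side by side**

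| First development of the effusion | 4.1.1 footnote 1 | Appendix III |
|---|---|---|
| During the procedure to day 30 after an ablation | inside window | inside window |
| Day 31 to about day 450, single procedure | inside window | outside |
| Day 211 to about day 450, repeat on day 180 | inside window | outside |

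Day 450 is the nominal 15-month visit (Protocol 6.6). Day 180 is the last day on which the TactiCath SE may be used for a repeat (Protocol 6.6.1), and 180 + 30 = 210. If Appendix III governs, the 15-month window does nothing for this component beyond 30 days after an ablation.

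The other two footnote 1 components do not have this problem. Atrioesophageal fistula has no time limit in Appendix III. Pulmonary vein stenosis is defined by degree alone ("Reduction of the diameter of a pulmonary vein or a pulmonary vein branch of" at least 70% on imaging).

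**2. Pericarditis with onset within 7 days**

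| Case | Footnote 2 | Appendix III |
|---|---|---|
| (a) Required admission of 24 h or less, or for observation only; symptoms 7 days or less | excluded | included |
| (b) Pleuritic symptoms for 8–30 days, no admission or other Appendix III criterion | included | excluded |
| (c) Stay prolonged by 24–48 h | arguable | arguable |

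Case (a) is the clear conflict. Protocol 7.1.2 lists in-patient hospitalisation among the outcomes that make an event serious, so such a case can be a serious adverse event. Case (b) matters only if the event is serious on another criterion, which is likely to be rare. Case (c) depends on how the hospitalisation wording is read.

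**3. Size, as an illustration**

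Inputs from the Protocol: performance goal 16.8% (8.2.1.1 and the sample-size text), 20% attrition, 224 subjects. Attrition step: 179 / 0.80 = 223.75, which rounds up to 224, so the implied evaluable number is 179. Alpha, the expected rate and the target power are redacted, so 224 itself cannot be fully reproduced.

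Exact binomial lower tail at p0 = 0.168, with alpha assumed:

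- n = 179: P(X ≤ 20) = 0.0236, P(X ≤ 21) = 0.0388, P(X ≤ 22) = 0.0609. The largest passing count is 20 at one-sided 0.025 and 21 at 0.05.
- n = 224: P(X ≤ 26) = 0.0198, P(X ≤ 27) = 0.0312, P(X ≤ 28) = 0.0474, P(X ≤ 29) = 0.0696. The largest passing counts are 26 and 28.

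Power is P(X ≤ limit | n = 179, p + d/179). Here d is the change in the expected number of cases, and the true rates p are assumptions.

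| True rate p | Limit 20, d = 0 | Limit 20, d = +2 | Limit 21, d = 0 | Limit 21, d = +2 |
|---|---|---|---|---|
| 6% | 99.7% | 98.3% | 99.9% | 99.1% |
| 7% | 98.6% | 94.3% | 99.3% | 96.6% |
| 8% | 95.0% | 86.0% | 97.1% | 90.7% |
| 9.5% | 81.6% | 65.2% | 87.2% | 73.4% |

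With d = −2 and limit 20, power rises from 98.6% to 99.8% at 7% and from 81.6% to 92.6% at 9.5%.

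**The case against.** The best defence on pericarditis is that the texts are layered: Appendix III describes a major complication, and footnote 2, which is worded exclusively and repeated in Appendix IV and SAP 1.4.1, restricts what is counted. That is a reasonable reading, but it is not a stated precedence. The Appendix III preamble claims to decide endpoint inclusion. The bleeding row also uses the major-complication wording ("if it requires and/or is treated with transfusion or results in a 20% or greater fall in hematocrit"), and footnote 3 uses the same words as the counting rule for bleeding. It can be answered that the bleeding component is itself listed as major bleeding, whereas the pericarditis bullet carries no such qualifier. This weakens the comparison without settling the question.

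The pericarditis conflict is also narrow. Protocol 7.1.2 requires a serious deterioration in health as well as a hospital stay, so some observation-only admissions would count under neither text. That stands.

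For tamponade/perforation, Appendix III could define the event while footnote 1 merely lifts the 7-day limit. Footnote 1 would then work for days 8–30, but its 15-month reach would still be empty after that.

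The CEC charter was not supplied and SAP 2.3.1.1 is largely redacted, so either may contain a rule. If so, adjudication may be settled in practice, but the CIP would still contradict itself.

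Finally, nothing in the documents supports two affected cases, and the table models them as a rate shift. Adding exactly two cases to the count at limit 20 gives 95.4% rather than 94.3% at 7%, and 87.3% rather than 86.0% at 8%. The message is unchanged.

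**Conclusion.** The concern holds. The current text contains two incompatible windows for tamponade/perforation and two incompatible rules for a short or observation-only pericarditis admission, with no readable statement of which prevails. The tamponade conflict is the stronger; the pericarditis conflict is real but narrow.

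The effect on the result cannot be estimated from the documents. It is negligible at low true event rates, can go in either direction and may be nil. It could change the conclusion only if the observed count falls near the pass limit. The power figures rest on the assumed alpha, the assumed true rates, 179 evaluable subjects and a shift of two cases. The textual conflict rests on none of these.

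**What to change.** Before the analysis, the sponsor should choose a single window for tamponade/perforation and a single counting rule for pericarditis. These should read the same in Protocol 4.1.1, Appendix III, Appendix IV, SAP 1.4.1 and the CEC charter, with a sentence saying which text governs if they differ. SAP 2.3.1.1 should be checked too, because its readable sentence gives 7 days without any exception.

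Since 4.1.1, Appendix IV and SAP 1.4.1 already agree, the shortest edit is to have the two Appendix III rows refer to the 4.1.1 footnotes for endpoint counting. If the sponsor prefers the Appendix III rules, the footnotes change instead. Any affected cases already adjudicated should be re-checked against the chosen rule. Reporting the safety count under both texts is an optional sensitivity line.

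The cost is wording in two rows and the charter, plus a re-check that may involve no cases. The reported safety rate could move slightly in either direction.
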